### Specific Aim 1: tDCS for executive dysfunction in mmTBI

Experiments in this aim will test the hypothesis that in patients with mmTBI, left prefrontal anodal tDCS concurrent with cognitive training for up to ten consecutive weekdays will result in significantly more improvement in executive function compared to sham stimulation. Patients with cognitive complaints 3 months to 15 years after mmTBI will be recruited from local emergency departments and brain injury clinics. Healthy controls will also be recruited through flyers, advertisements and word of mouth. Aim 1.1: tDCS will be paired with computer-based cognitive training tasks of response inhibition, set shifting, and working memory, while executive function will be measured with the NIH Examiner battery before, immediately after, and one month after stimulation. Pre-and post-stimulation EEG and MRI may be obtained. During EEG and MRI participants may be asked to rest quietly or perform simple tasks. Aim 1.2: Persistence of post-traumatic symptom reduction and quality of life improvement will be assessed with Common Data Elements instruments via telephone interview at 6 months and one year. Aim 1.3: Clinical predictors of tDCS response including EEG frontal theta synchrony, injury severity, presence of neuroimaging abnormalities, premorbid intelligence, and post-traumatic symptom burden will be determined with linear mixed-models analysis.

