*Cognitive control Tasks:* Participants may be administered the cognitive training battery for 30 minutes, during treatment and sham. Session procedures will begin with tDCS electrode placement while seated in a comfortable chair. After initiation of tDCS, the cognitive training will be administered on a laboratory computer. The two tasks will be presented for 15 minutes each, in counterbalanced alternating order over the ten sessions. The tasks to be coupled with tDCS are the AX-CPT (set shifting/response inhibition) and a dual auditory/visual N-back task (working memory), and were selected based on their activation of the critical neural networks associated with the three executive functions of interest. AX-CPT is a continuous performance task in which subjects must respond to specific paired letter combinations (A followed by X) with a button press while inhibiting response to non-target combinations (AY, BY, BX) (Figure 8). The dual N-back task is a continuous performance test in which subjects respond to simultaneous sequences of visuospatial and auditory stimuli being presented that match preceding stimuli n-steps earlier in the sequence.

Specific Aim 1.2: Persistence of tDCS effects and quality of life

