#### Experimental Design and Methods

*Participants:* TBI subjects from Aim 1.1 will be carried forward for study in Aim 1.3. Key clinical variables in the study group will be analyzed for association with tDCS effect, namely, lesser post-traumatic symptom burden as measured by the NSI, mild versus moderate severity of TBI, lack of neuroimaging abnormalities on MRI, and higher premorbid level of intelligence as measured by the WTAR, as these are factors shown to predict better recovery from TBI.

Specific Aim 2.1: Effectiveness of tDCS for depression after mmTBI

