### Specific Aim 2.2:

The subjects from Aim 2.1 will be automatically included. At 6 months and 1 year after stimulation, subjects will be contacted via telephone and administered the depression assessment tools utilized before, immediately after, and 1 month after stimulation.

**Specific Aim 2.3:** Subjects from Aim 2.1 will be carried forward for study in Aim 2.3. Patient and injury characteristics will predict positive response to tDCS, namely, higher premorbid intellectual function (WTAR), lesser severity of injury (mild versus moderate), lack of neuroimaging abnormalities on MRI, and more severe pre-stimulation depressive symptoms (BDI, HAM-D). Understanding which of the clinical variables described above moderate the efficacy of tDCS in mmTBI will allow for more precise patient selection and better overall efficacy in future applications.

Each of the 80 participants will receive \$20/hr in the form of cash cards for taking part in the study.. This is felt to be a fair amount that is not coercive and will help decrease attrition for this study which involves many visits.

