Statistical analyses will utilize the CTSC Biostatistics core. Power analyses and statistical analysis strategy were determined with our statistician [name], who will continue to provide recommendations and support throughout the project. Sufficient group sizes were determined on the basis of data derived from preliminary studies. Clark and colleagues found an effect size of Cohen's  $d = 1.2$  for tDCS to induce improvements in cognition. For our power calculations we will assume a more conservative effect size of  $d = 0.7$  which is consistent with a recent meta-analysis of tDCS effect sizes. With 40 tDCS treatment patients compared to 40 sham patients and an effect size of 0.7, we have 80% power to detect effects of active versus sham treatment in a two-sample t-test. Power in the linear mixed model analysis should be superior that that of the t-test. For Aim 1.1, the central analyses evaluate group (active vs. sham) differences in the EEG data and on the three Examiner composite variables across the three initial time points (before, immediately after, and 1 month after tDCS stimulation protocol). To test this hypothesis, three separate linear mixed models analyses will be performed using the three Examiner composite scores (Fluency, Cognitive Control, Working Memory) as dependent variables. In each analysis, we will incorporate three covariates that may predict variation in learning (severity: mild vs. moderate, premorbid intelligence: WTAR score, and symptom burden: NSI). This will allow us to determine predictors of treatment response (Specific Aim 1.3). Sex, ethnicity, and age will also be entered into the statistical model. The effects of these covariates will be estimated by constructing appropriate contrasts in model effects. A similar set of analyses will evaluate group differences on the variables assessed in our long-term oral/phone follow-up (five data points: (1) before tDCS, (2) immediately after tDCS, (3) 1 month post-tDCS, (4) 6 months, and (5) 1 year) for Aim 1.2. For these analyses dependent variables will be the total cognitive items score of the NSI and the PROMIS-29 profile total score). Significant effects will be followed up with more fine-grained analysis of the components of composite scores. The use of linear mixed-models minimizes the adverse impact of a missing data point, which may well occur in a longitudinal clinical study such as this. Expected attrition will be taken into account with an intention-to-treat analysis. Missing data patterns will be analyzed to assess the extent to which they are informative (in contrast to missing at random), and analyses adjusted accordingly. All EEG data will undergo standard preprocessing (e.g. motion correction, spatial normalization) and quality control prior to statistical modeling. Depending on the specific question of the study, data may be analyzed using the general linear model, independent components analysis, machine learning techniques, or a variety of other standard approaches for neuroimaging data.

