We will also provide all participants and their families with a referral list of community support, treatment, and educational resources about TBI. This information will also be explained during the consent process. In addition, if a participant's status with respect to any of the study criteria change during the experiment (i.e., initiation of substance abuse), the participant's participation in the study may be terminated without their consent. Our consent form will include a statement regarding anticipated circumstances under which the subject's participation may be terminated by the investigator without regard to the subject's consent and a statement indicating that significant new findings developed during the course of the research which may relate to the subject's willingness to continue participation will be provided.

Statistical analyses will utilize the CTSC Biostatistics core. Power analyses and statistical analysis strategy were determined with our statistician [name], who will continue to provide recommendations and support throughout the project. For Aim 1.1, the central analyses evaluate group (active vs. sham) differences on the three Examiner composite variables across the three initial time points (before, immediately after, and 1 month after tDCS stimulation protocol). To test this hypothesis, three separate linear mixed models analyses will be performed using the three Examiner composite scores (Fluency, Cognitive Control, Working Memory) as dependent variables. In each analysis, we will incorporate three covariates that may predict variation in learning (severity: mild vs. moderate, premorbid intelligence: WTAR score, and symptom burden: NSI). This will allow us to determine predictors of treatment response (Specific Aim 1.3). Sex, ethnicity, and age will also be entered into the statistical model. The effects of these covariates will be estimated by constructing appropriate contrasts in model effects. A similar set of analyses will evaluate group differences on the variables assessed in our long-term oral/phone follow-up (five data points: (1) before tDCS, (2)

**PROTOCOL TITLE:** Transcranial direct current stimulation for treatment of deficits after traumatic brain injury.

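### The plan says covariates will identify predictors of tDCS response (Aim 1.3), but names no arm-by-predictor term, so as written it cannot answer that question

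*Combined protocol and SAP*

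**What the plan says.** Section 11 describes three linear mixed models, one per Examiner composite, comparing active with sham over three time points. On predictors it says "In each analysis, we will incorporate three covariates that may predict variation in learning" and lists severity (mild or moderate), WTAR and NSI. The next sentence is "This will allow us to determine predictors of treatment response (Specific Aim 1.3"). Sex, age and ethnicity are added. The only further detail, in Sections 11 and 14 alike, is "The effects of these covariates will be estimated by constructing appropriate contrasts in model effects".

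The questions are set elsewhere:

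- Section 10, Specific Aim 1.3: "Key clinical variables in the study group will be analyzed for association with tDCS effect".
- Section 10, Specific Aim 2.3: "Understanding which of the clinical variables described above moderate the efficacy of tDCS in mmTBI" is to guide patient selection in later use. Its predictors include "more severe pre-stimulation depressive symptoms (BDI, HAM-D").
- Section 1, Specific Aim 1: "Clinical predictors of tDCS response including EEG frontal theta synchrony", among others, to be examined with a linear mixed model.

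Section 10 says of the training tasks: "Participants may be administered the cognitive training battery for 30 minutes, during treatment and sham".

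**The concern.** The covariate sentence and the aim are about different quantities. A covariate effect describes participants whichever arm they are in. A predictor of response to tDCS describes how the active-minus-sham difference changes with that characteristic. The documents name no term that combines arm and predictor.

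The distinction matters here because the training may be given in both arms. Someone with a high WTAR score may gain more from two weeks of training whether the current is active or sham. If the sentence in Section 11 is followed literally, that person's characteristic can be reported as a predictor of benefit from tDCS, and Aim 2.3 intends such results to inform patient selection.

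**Working it through.** **1. What each term estimates.** Let C be a participant's mean of the two post-stimulation scores minus baseline, A the arm (0 sham, 1 active) and x a standardised baseline predictor. Let s0 and s1 be the slopes of C on x in the sham and active arms.

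- Question in Aims 1.3 and 2.3: does the tDCS effect depend on x? The quantity is s1 − s0, the arm-by-time-by-predictor contrast.
- Covariate-by-time effect with equal arms: (s0 + s1)/2.
- Covariate effect: the corresponding average slope on the level of the score.

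If s0 = s1 = 0.2, the quantity asked about is 0, while the covariate-by-time effect is 0.2.

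**2. The plan's own power figure.** Section 11 gives 80% power for 40 versus 40 at d = 0.7 by t-test. Alpha is not stated. The noncentral t gives 87.1% at two-sided 0.05 and 79.9% at two-sided 0.025; 33 per arm gives 79.97% at 0.05. This figure concerns the main comparison and does not bear on the present point. No power is given for any predictor analysis.

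**3. How often the wrong label could be attached.** From the plan: 40 per arm, d = 0.7, three time points. Assumed: two-sided 0.05, residual SD 1 at each time point, compound symmetry with within-person correlation ρ of 0.5 to 0.7, complete data, one predictor.

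Var(C) = (1 + ρ)/2 + 1 − 2ρ = 1.5(1 − ρ), that is 0.75 at ρ = 0.5 and 0.45 at ρ = 0.7.

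SE of the covariate-by-time slope = √(Var(C)/80) = 0.097 and 0.075. For a slope of 0.2, slope/SE = 2.07 and 2.67. The normal approximation gives rejection in about 54% and 76% of trials. Simulation (20,000 trials, t-test) gives 52% and 74%.

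| True situation (s0 / s1) | Covariate-by-time flags it, ρ 0.5 / 0.7 | Arm-by-time-by-predictor flags it, ρ 0.5 / 0.7 |
|---|---|---|
| Equal learning, 0.1 / 0.1 | 17% / 26% | 5% / 5% |
| Equal learning, 0.2 / 0.2 | 52% / 74% | 5% / 5% |
| Equal learning, 0.3 / 0.3 | 84% / 97% | 5% / 5% |
| Active arm only, 0 / 0.5 | 66% / 84% | 69% / 89% |

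If the covariate effect is instead read on a single post-treatment score (residual SD 1), a purely prognostic slope of 0.2 is flagged in 41% of trials, against 5% for the arm-by-covariate term. A constant prognostic effect, the same at all three times, is not wrongly flagged by covariate-by-time (5%).

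**4. What the right contrast can deliver.** For severity with a proportion p mild (not given in the documents; assumed), SE = √Var(C) × √(2/(40p) + 2/(40(1 − p))). Example: p = 0.5, ρ = 0.5 gives 0.866 × 0.447 = 0.387. Power is for a 0.7 SD difference in tDCS effect between mild and moderate TBI (noncentral t, 76 df).

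| Mild | SE, ρ 0.5 / 0.7 | Power | 95% CI half-width (SD) |
|---|---|---|---|
| 50% | 0.387 / 0.300 | 43% to 63% | 0.77 / 0.60 |
| 80% | 0.484 / 0.375 | 30% to 45% | 0.96 / 0.75 |
| 90% | 0.645 / 0.500 | 19% to 28% | 1.29 / 1.00 |

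**The case against.** The strongest reply is that the plan is silent rather than wrong. The models compare arms over time, the sentence on contrasts in model effects could cover an arm-by-predictor contrast, and the aims state the moderation question plainly. This stands in part: a reader might infer that the sponsor intends main effects only, and the documents do not show that. But the sentence on contrasts refers to the effects of the covariates, and no contrast can recover an arm-by-predictor effect unless the product term is in the model. The error rates above apply only if a weaker term is used.

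Second, the harm depends on the scenario. A reader might infer that real modifiers would generally be missed. They would not: one acting only in the active arm is found nearly as often by either term. Missing one requires slopes that largely cancel between arms, which nothing in the documents suggests. The false-positive risk remains.

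Third, a reader might take the absence of EEG theta and imaging abnormality from the covariate list as an oversight. EEG is planned in a subset and MRI in a subgroup, so leaving them out of models for all participants is understandable, and Section 2 separately plans to correlate response with EEG measures. Likewise, one might infer that baseline depression would be flagged through regression to the mean. No text enters baseline BDI-II or HAM-D as a covariate, and the carry-over of the Aim 1 models to Aim 2 is itself only possible, so that is not a defect of the written plan.

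Finally, an arm-by-time-by-predictor term over three categorical time points has 2 degrees of freedom and no single estimate. Its power for severity would be about 34% to 53%, 23% to 36% and 15% to 22% at 50%, 80% and 90% mild. This objection stands, and the fix must name one contrast.

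**Conclusion.** The point holds: the analysis stated for Aim 1.3 does not answer Aim 1.3, because the term that carries the answer is not named. Under the assumptions above, following the sentence literally would label a factor that predicts learning equally in both arms (0.2 SD per SD) as a predictor of tDCS response in about 52% to 74% of trials, instead of 5%. The size depends on the assumed slope and correlation; the mismatch between term and question does not.

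A reader might go further and conclude that the trial's main result is compromised, or that the objectives must be rewritten. Neither follows. The primary active-versus-sham comparison is untouched, and low power for moderation can be reported without changing the aims. This should be corrected before analysis, but it does not threaten the trial.

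**What to change.** In Sections 11 and 14, keep severity, WTAR and baseline NSI as adjustment covariates. NSI is measured repeatedly, so say that the baseline value is meant. Replace the sentence quoted from Section 11 with text such as:

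> For Aim 1.3, each baseline predictor (severity, WTAR, NSI) is tested in the TBI participants by adding arm-by-time-by-predictor terms to the mixed model. The estimate reported, with its 95% CI, is the arm-by-predictor contrast on the mean of the two post-stimulation scores minus baseline. It is interpreted as exploratory.

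For Aim 2.3, state that the same contrast is applied to BDI-II and HAM-D over the first three time points, with baseline BDI-II and HAM-D among the predictors. Test EEG theta and imaging abnormality in the same way, only in the subset with those data.

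The change uses data already planned and adds model terms, not visits or participants. Its price is imprecision: for severity, a 95% CI half-width of about 0.6 to 1.3 SD, and power of 43% to 63% at best for a 0.7 SD difference. The plan should state this next to the analysis.

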
## 12. Provisions to Monitor the Data to Ensure the Safety of Subjects

Data safety and monitoring will be carried out to ensure and maintain the scientific integrity of this project and to protect the safety of our participants. Safety monitoring is the process during the study that involves review of accumulated outcome data for groups of subjects to determine if any of the procedures practiced should be altered or stopped. Ultimately, the PI ([name]) will be responsible for monitoring the safety of the study and complying with the reporting requirements. An independent Data Safety and Monitoring Board (DSMB) will review the study data on a quarterly basis with the PI to ensure participant safety. The DSMB for this study will be composed of [name], the medical director of the Electroconvulsive Therapy Service at UNM, and [name], staff epileptologist of the Epilepsy Monitoring Unit at UNM. Their experience in assuring safety of brain stimulation therapies and seizure monitoring protocols make them ideally suited to serving on this project's DSMB. Continuous, close monitoring of participant safety will include prompt and frequent reporting of safety data (i.e., adverse/serious adverse events) to the

**PROTOCOL TITLE:** Transcranial direct current stimulation for treatment of deficits after traumatic brain injury.

DMSB, the University of New Mexico Health Sciences Center Institutional Review Board (UNMHSC IRB) and/or appropriate NIH staff with oversight responsibility. The PI will provide a summary of the safe conduct of the study to NIH on an annual basis as part of the progress report. All AEs occurring during the course of the study will be collected, documented, and reported to the UNMHSC IRB.

The review of data may result in early termination of the study, amendment to the protocol, or changes to the data collection plan or study forms if it appears that there are adverse events occurring at a rate significantly greater than that found in similar tDCS studies involving subjects with neurological disorders (ie. stroke). Should the protocol or data collection plans or study forms be amended as a result of data review, the IRB will be notified and the amendment approved prior to study amendment implementation. In addition, the participants will be notified of any significant new findings that develop during the course of research that may affect their wish to continue participation in the study.

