Randomization will occur at time of consenting. The study coordinator who consented the patient will use a coin-tossing procedure to determine whether the subject is assigned to the active group (group 1) or control group (group 2). Modifications will be made as necessary toward the end of enrollment to ensure equal group size and balanced distribution of demographic variables such as age and gender. The study coordinator will not be blinded to group assignment, and with the assistance of the Clinical Core, will program the TDCS devices to deliver active or sham stimulation depending on which group the subject has been assigned. However, the coordinator will not be involved in performing any stimulation procedures. The study technician and principle investigator, who will be responsible for administering the stimulation, will not be aware of which group receives active versus control, and will thus be blinded, as the TDCS device will only display the group number (1 or 2).

Once group membership is determined, individual participants may undergo demographic data collection, neuropsychological assessments and tDCS treatment sessions. They may also undergo EEG and/or MRI. Direct identifiers of participants will be maintained on a separate database that will be stored behind locked doors, in a locked filing cabinet in a secure area of the Clinical Core.

**Demographic Data:** As part of the initial assessment, basic demographic data regarding the subject may be noted down, including age, gender, socioeconomic status, educational attainment, handedness, use of common stimulants such as caffeine, and brain injury severity. They may also be asked if they are willing to allow their medical record to be accessed, for the purposes of confirming details about any TBI as well as obtaining results of neuroimaging studies done at the time of injury or afterward. This will include medical, surgical, neurological and psychiatric history, results of lab tests, brain scans, electroencephalography tests, medication lists, information from doctor's visits and hospital visits.

**Neuropsychological testing procedures:** All neuropsychological testing will be administered in the Center for Brain Recovery and Repair Core by trained study personnel under direct supervision of core directors, clinical neuropsychologists Drs. [name], [name], or the PI. The primary dependent outcome variables to be studied are the three composite scores generated by

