- 4) It is not for a use of substantial importance in diagnosing, curing, mitigating, or treating disease, or preventing impairment of human health

According to the FDA, serious adverse events are those in which the outcome is death, life-threatening, hospitalization, disability/permanent damage, congenital anomaly, requiring intervention to prevent permanent impairment, or other serious events such as refractory seizures, cardiorespiratory arrest, or anaphylactic reaction. No serious adverse events attributable to TDCS have been reported in the more than 10,000 subjects investigated in the contemporary TDCS literature since 1998. This literature includes studies in patients with severe brain injury, stroke, epilepsy, and neurodegenerative disorders, none of whom have been reported to experience serious adverse events. Specifically, there have been no reports or evidence presented of damage to the brain, seizures, or cardiorespiratory arrest. Animal studies of charge densities necessary to induce brain damage in rats were found to be 100 times higher than the charge density used in TDCS trials with standard parameters (< 2.5 mA, no more than 2 sessions daily, < 60 min per session, use of electrodes that minimize skin burns) as determined by world-wide expert consensus. The commonly reported side effects of TDCS are itching, burning, tingling, headache, and discomfort (10-40%), all of which are mild and transient. As this trial will be operating within standard parameters as defined

PROTOCOL TITLE: Transcranial direct current stimulation for treatment of deficits after traumatic brain injury.

above, we believe our use of TDCS in subjects with mild-moderate traumatic brain injury represent a Non-Significant Risk.

PROTOCOL TITLE: Transcranial direct current stimulation for treatment of deficits after traumatic brain injury.

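### The study-level safety trigger in Section 12 rests on an unspecified outside adverse-event rate, and the review as described does not use the trial's own sham arm

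*Combined protocol and SAP*

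**What the plan says.** Section 12 (Provisions to Monitor the Data to Ensure the Safety of Subjects) describes safety monitoring as "review of accumulated outcome data for groups of subjects to determine if any of the procedures practiced should be altered or stopped". A Data Safety and Monitoring Board will "review the study data on a quarterly basis with the PI to ensure participant safety". The action clause is advisory: "The review of data may result in early termination of the study, amendment to the protocol", or changes to data collection, if there appear to be "adverse events occurring at a rate significantly greater than that found in similar tDCS studies involving subjects with neurological disorders", with stroke as the example. All adverse events are collected, with no filter by type, grade or relatedness. This is the only study-level criterion in the protocol.

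The rates that could serve as the reference are elsewhere, and they describe different things:

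- **Section 16, stroke:** a statement in words that side effects were not increased; no rate.
- **Section 16, TBI:** no adverse events in 37 patients with moderate to severe injury.
- **Section 31, serious events:** "No serious adverse events attributable to TDCS have been reported in the more than 10,000 subjects" in the contemporary literature.
- **Section 31, common events:** "The commonly reported side effects of TDCS are itching, burning, tingling, headache, and discomfort (10-40" per cent), described as mild and transient, for tDCS generally.

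Section 10 (Participants) assigns 40 TBI subjects and 40 healthy controls to each of active and sham. Section 10 also says that the PI and the technician "will not be aware of which group receives active versus control", while the study coordinator is unblinded. Sections 10 and 18 label active as group 1 and sham as group 2.

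**The concern.** A criterion worded as "occurring at a rate significantly greater than" some reference needs the reference. Here the comparator named is stroke studies, for which the protocol gives no figure, and nothing says which of its other figures would apply to which events. Half of the randomized subjects are healthy controls, for whom studies in neurological disorders are not an obvious reference either.

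A concurrent comparator already exists. The sham arm is randomized 1:1 and shares the trial's population, visits and session length, and the ten-minute symptom checks are described for stimulation sessions without distinction by arm. No section plans an active-versus-sham comparison of adverse events.

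The review format adds a difficulty. The board meets with a PI who must stay blind, and no closed session is described. On that description the board either goes without by-arm data or receives it in a meeting that puts the PI's blind at risk.

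At stake is whether an excess of common events on active stimulation in people with brain injury would be recognised on a consistent basis, or judged by whichever outside figure comes to hand.

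**Working it through.** The protocol gives no threshold to reproduce, so the check asks how far the trigger moves with the reference.

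**Inputs from the documents.** 40 active and 40 sham TBI participants (Section 10); reference rates of 10% and 40% as the ends of the range for common effects (Section 31); 0 of 37 (Section 16); 0 in more than 10,000 for attributable serious events (Section 31).

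**Assumptions, because Section 12 is silent.** Events counted as participants with at least one; exact binomial test; one-sided 0.025; a single look. One-sided 0.05 is shown as a sensitivity.

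**1. Trigger count.** Smallest r with P(X ≥ r) ≤ 0.025, X ~ Bin(40, p0).

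- p0 = 0.10: P(X ≥ 8) = 0.042, P(X ≥ 9) = 0.015, so r = 9 (9/40 = 22.5%).
- p0 = 0.40: P(X ≥ 22) = 0.039, P(X ≥ 23) = 0.019, so r = 23 (23/40 = 57.5%).

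At one-sided 0.05 the counts are 8 and 22.

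**2. Chance of firing if the true active rate is 30%.** With X ~ Bin(40, 0.30), P(X ≥ 9) = 0.889 and P(X ≥ 23) = 0.0003. At one-sided 0.05, P(X ≥ 8) = 0.945 and P(X ≥ 22) = 0.0009. The same true rate is almost always or almost never flagged, according to the reference.

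**3. The TBI reference.** The three studies described in Section 2 contribute 5 + 9 + 23 = 37 patients, matching Section 16. The one-sided 95% upper bound for 0/37 is 1 − 0.05^(1/37) = 7.8%, so this base is too small to establish a rate near zero.

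**4. Serious events.** For 0 in 10,000 the approximate 95% upper bound is 3/10,000 = 0.03%. At that rate, P(at least 1 of 40) = 1 − 0.9997^40 = 1.2%, so one attributable case already exceeds the reference. If the true rate were 5%, the chance of seeing at least one case is 1 − 0.95^40 = 87%.

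**5. What a sham comparison could do.** Power of a one-sided Fisher exact test, 40 per arm:

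| Active vs sham | alpha 0.05 | alpha 0.025 |
|---|---|---|
| 30% vs 10% | 66% | 53% |
| 20% vs 10% | 24.5% | 16% |
| 5% vs 0% | 5% | 1% |

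As an estimate with an interval it is still informative. For an illustrative 12/40 against 4/40, the difference is 0.30 − 0.10 = 0.20, with standard error √(0.30×0.70/40 + 0.10×0.90/40) = 0.087 and 95% CI 0.20 ± 1.96×0.087, about 3 to 37 percentage points.

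All counts and rates here illustrate sensitivity. None is proposed as a stopping level.

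**The case against.** The clause is advisory and leaves judgement to a board with brain-stimulation and epilepsy expertise. Section 12 also requires prompt reporting of adverse and serious adverse events to the board, the IRB and/or NIH, and Sections 10, 13 and 16 contain stopping rules for the individual session. This stands, and it lowers the stakes. It does not supply the missing reference or a by-arm view, and the individual rules do not detect an excess across the trial.

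Sham is also an imperfect comparator. It delivers up to 0.2 mA for 30 minutes and is meant to feel similar, so harms shared by both arms, such as electrode or skin problems, cancel in the difference. Power is low, as shown above. This also stands, and is why outside rates should be kept.

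Four stronger readings are tempting, and the documents do not support them.

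- **That the reference spans zero to 40%.** The zeros concern adverse events in a small TBI series and attributable serious events in the wider literature; 10-40% concerns mild, transient effects. These are different event classes. The accurate statement is that the reference is undefined.
- **That the trigger cannot work.** For a seizure or other serious event the reference is effectively zero and a single attributable case stands out. There it is the sham comparison that lacks power.
- **That the board sees only pooled data.** Section 12 refers to groups of subjects and does not say which groups. Tables by coded group are not ruled out.
- **That pooling would necessarily hide an excess.** With 30% on active and 10% on sham, the expected pooled count is 16/80. Against 10% at one-sided 0.025 the trigger is 15/80, so 16 fires it; the chance of reaching 15 is about 66%. The rule is silent on 16/80 against higher references (24/80 needed at 20%, 42/80 at 40%). This is the same dependence on the reference, not a separate failure.

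**Conclusion.** The concern holds for common adverse events. The only study-level criterion depends on an outside rate that the protocol does not specify. Across the range it quotes for common effects, the trigger for 40 active TBI participants moves from 9 to 23, and the chance of flagging a true 30% rate moves from 89% to under 0.1%. These figures rest on an assumed one-sided 0.025 exact test at a single look; at 0.05 the counts are 8 and 22 and the conclusion is the same. Quarterly looks would add multiplicity that Section 12 does not address.

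It is also a real weakness that no active-versus-sham comparison of adverse events is planned, and that the board's review is described only as a meeting with the blinded PI. The concern does not extend to serious events, where an outside rate near zero is a workable reference. The change is worth making before the first board review.

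**What to change.** Amend Section 12 as follows.

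- Each quarter the board receives adverse-event tables by arm, prepared by the already unblinded coordinator or a statistician, in a session closed to the PI. TBI and healthy-control subjects are best shown separately.
- For common events, the tables give the active-minus-sham difference with its 95% CI, as information for judgement and not as a significance gate.
- Case-by-case review of serious events and the outside rates stay alongside, because the sham comparison is underpowered for rare events and blind to harms common to both arms.
- Before the first review, the sponsor and board record in writing the event classes and, for each, the reference rate and its source. Any level of concern is theirs to set; none is suggested here.

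The cost is a change of wording and one extra table per quarter. The downside is that the board becomes unblinded, so by-arm results must not reach the PI or the technicians.
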